1. STUDY SUMMARY

PROTOCOL TITLE	Study of ¹⁸ F-DCFPyL PET/CT in the Assessment of Patients with Renal Cell Carcinoma
IRB NUMBER	IRB00075596
J Number	J15145
IND NUMBER	121064
INVESTIGATIONAL AGENT	¹⁸ F-DCFPyL
PATIENT POPULATION	Patients with localized high-risk (T2-4N0M0) or metastatic (T _{any} N1M0 or T _{any} N _{any} M1) renal cell carcinoma
SAMPLE SIZE	N = 35
OBJECTIVES	
 • To investigate the sensitivity of ¹⁸F-DCFPyL PET/CT for detecting sites of disease in patients with localized high-risk (T2-4N0M0) or metastatic (T_{any}N1M0 or T_{any}N_{any}M1) renal cell carcinoma. • To correlate sites of radiotracer uptake on ¹⁸F-DCFPyL PET/CT with conventional imaging findings. • To correlate sites of radiotracer uptake on ¹⁸F-DCFPyL PET/CT with locations of disease recurrence/progression. • To correlate sites of radiotracer uptake on ¹⁸F-DCFPyL PET/CT with the histology of biopsied or resected tissue specimens. • To correlate findings on ¹⁸F-DCFPyL PET/CT with duration of progression-free survival.

In this pilot study we aim to expand upon the limited existing data on PSMA PET/CT of RCC by imaging a cohort of patients with kidney cancer over a range of disease stages (stage II-IV) and without restriction to the clear cell histologic type. These preliminary data may then serve to aid in hypothesis generation for the planning of future studies.

3. OBJECTIVES

- To investigate the sensitivity of ¹⁸F-DCFPyL PET/CT for detecting sites of disease in patients with localized high-risk (T2-4N0M0) or metastatic (T_{any}N1M0 or T_{any}N_{any}M1) renal cell carcinoma.
- To correlate sites of radiotracer uptake on ¹⁸F-DCFPyL PET/CT with conventional imaging findings.
- To correlate sites of radiotracer uptake on ¹⁸F-DCFPyL PET/CT with locations of disease recurrence/progression.

- To correlate sites of radiotracer uptake on ¹⁸F-DCFPyL PET/CT with the histology of biopsied or resected tissue specimens collected during the course of routine clinical care.
- To correlate findings on ¹⁸F-DCFPyL PET/CT with duration of progression-free survival.

4. PATIENT SELECTION & ELIGIBILITY

4.1. NUMBER OF PATIENTS

During the course of this study we aim to enroll 35 patients

4.2. INCLUSION CRITERIA

1. Age ≥18 years
2. Clinically diagnosed or histologically proven stage II-IV (T2-4N0M0, T_{any}N1M_{any}, T_{any}N_{any}M1) renal cell carcinoma
3. Completed staging evaluation with CT or MRI of the chest, abdomen and pelvis ≤90 days prior to study enrollment

4.3. EXCLUSION CRITERIA

1. History of other malignancy diagnosed within the last 3 years (with the exception of low risk prostate cancer [Gleason score 6, pretreatment PSA ≤10, cT2a or pT2 if treated], DCIS of the breast, squamous cell carcinoma or basal cell carcinoma of the skin)
2. Administered a radioisotope within 5 physical half-lives prior to study enrollment
3. Pregnancy (as determined in accordance with the policies of the PET center)
4. Intention to enroll in a blinded therapeutic clinical trial following PET/CT

4.4. INCLUSION OF WOMEN AND MINORITIES

Men and women of all races and ethnic groups are eligible for this study and encouraged to participate.

5. SUBJECT RECRUITMENT AND INFORMED CONSENT

Urologists and medical oncologists at Johns Hopkins will be educated about the study including patient eligibility criteria. At the treating physician's discretion, patients will in turn be informed about the study and their interest in participation assessed. Any patient who expresses interest in participating in the study will then either be directly introduced to the study team staff, who will be present on select clinic days, or their contact information provided to the study coordinator. In all cases, as much time as is needed to consider study participation will be allowed to possible participants; resulting in multiple phone calls, visits, emails, or other communication, as necessary.

The principal investigator or designated individual will discuss the study with interested patients. Patients will be provided with the Institutional Review Board (IRB) approved consent form for review and given sufficient time to consider participation in the study. Once a decision has been made to enter into the study, a signature will be obtained from the patient to confirm consent.

Patients may voluntarily withdraw consent at any point following enrollment in the study. At the time of informed consent patients will be instructed that they may withdraw consent by contacting the principal investigator or study coordinator.

6. RISKS & BENEFITS

6.1. RISKS

¹⁸F-DCPyL is a novel imaging agent, which to date, has been studied in <50 patients at Johns Hopkins under existing IRB protocols (IRB00046315, IRB00062296, NA_00092956). Despite this small number, the compound appears to be very well tolerated with no reported serious adverse related events.

During the course of this study patients will be exposed to 1.59 rem of radiation. The risks related to both ¹⁸F-DCFPyL and radiation exposure will be explained to the patient during the informed consent process.

6.2. BENEFITS

There will be no direct medical benefit to participants participating in this study. Rather, their participating may help patients in the future by further our knowledge of RCC.

7. STUDY PROCEDURES

1. Eligability screening
2. Informed consent
3. Completion of data collection sheet, KPS score, ECOG performance status and FKSI-19 questionnaire
4. ¹⁸F-DCFPyL PET/CT scan
5. Assessment of adverse events via phone call at 1-3 days following PET/CT
6. Treatment per the treating physician including imaging as clinically indicated
7. Collection of clinic notes, surgical reports, imaging test results/images, pathology reports and pathology/tissue specimens in the form of slides or paraffin blocks which are generated as part of routine clinical care for up to five years following study enrollment

8. PROTOCOL FOR ¹⁸F-DCFPYL PET/CT

1. Patient will fast for 4 to 6 hours prior to injection of ¹⁸F-DCFPyL
2. An intravenous peripheral intravenous catheter will be placed (or an upper-extremity existing central line accessed) in order to inject the radiotracer
3. Intravenous fluid (5% dextrose + 0.45% normal saline) will be delivered at a low flow rate during the duration of the study (maximum 2 liters)
4. A bolus of less than or equal to 9 mCi (333 MBq) of ¹⁸F-DCPyL will be injected into the IV line by slow push
5. At approximately 60 minutes after the administration of ¹⁸F-DCFPyL, IV fluids will be discontinued and the patient will be asked to void. A whole-body CT and PET scan will then be acquired from the mid-thigh to the vertex of the skull. The PET/CT will be performed on a Discovery DRX PET/CT scanner (GE Healthcare) operating in 3-dimensional emission acquisition mode. Scans will include approximately 8 to 9 fields-of-view, depending on patient height.
6. Temporary IV access will be removed

9. STUDY STATISTICS

Descriptive statistics (i.e. proportions/percentages for categorical and medians with interquartile ranges for continuous variables) will be used to describe the study cohort and findings on ¹⁸F-DCFPyL PET/CT scans. More specifically, data will be reported on patient age, race/ethnicity, TNM stage, histologic RCC subtype, Fuhrman grade, surgical margin status, sites/burden of disease, prior cancer treatment and interval treatment following PET/CT scan. Additionally we will report the number and location of putative sites of disease detected on PET/CT. These sites will be correlated to findings on available conventional imaging as well as with histology of biopsied/resected tissue specimens obtained during the course of routine clinical care. Lastly, we will explore the relationship of PET/CT findings with the location and pattern of recurrence/progression as well as duration of progression-free survival. For any analysis of progression-free survival, Kaplan-Meier estimates will be calculated and groups will be compared with the log-rank test. Given the exploratory nature of this study, we do not have any predefined analyses in mind. We do envision, however, comparing the progression-free survival of patients after dichotomization/grouping by a number of different imaging parameters such as number of sites of disease, location of disease sites and mean SUV_{max} values.

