12. DISCLOSURE OF DATA

The results of ¹⁸F-DCFPyL PET/CT scans will be made available to both patients and treating physicians. Because this is a novel diagnostic test which is being studied under an IND, the following statement will appear in all radiology reports:

¹⁸F-DCFPyL PET/CT is currently being studied under an Investigational New Drug application from the United States Food and Drug Administration. This scan is considered experimental and the results should be interpreted in this context. Any treatment decisions made based on the results of this study should include a discussion with the patient as to the investigational nature of the scan and the possibility of basing management decisions on falsely positive and/or negative findings.

Additionally, at the time of informed consent, it will be explained to patients that the results of these scans may prompt additional confirmatory imaging and/or invasive procedures that would not have otherwise been contemplated had the patient not participated in this study.

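### Nothing in the plan keeps the PET/CT read independent of the staging CT/MRI it is compared with; if the reader has that imaging, agreement and CT/MRI-based sensitivity would tend to be overestimated

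*Combined protocol and SAP*

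**What the plan says.** Section 3 opens its list of objectives with "To investigate the sensitivity of" the PET/CT for sites of disease. The second objective is correlation of uptake with conventional imaging.

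The comparator comes first in time. Inclusion criterion 3 (Section 4.2) requires "Completed staging evaluation with CT or MRI of the chest, abdomen and pelvis ≤90 days prior to study enrollment".

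The PET result is described in two places:

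- Section 9: "we will report the number and location of putative sites of disease detected on PET/CT", followed by "These sites will be correlated to findings on available conventional imaging as well as with histology of biopsied/resected tissue specimens".
- Section 12: results "will be made available to both patients and treating physicians", with a caution about investigational status: "the following statement will appear in all radiology reports".

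Section 7 lists the study procedures without an interpretation step. Section 8 covers preparation, injection and acquisition, and ends with removal of the IV line. Neither these sections nor Section 9 says who reads the scan, what counts as a positive site, in what order images are opened, or whether the reader may see the staging CT/MRI.

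**The concern.** Sensitivity and agreement between two imaging methods mean what they appear to mean only if the calls on one are made without knowledge of the other. A reader who knows where the CT/MRI lesions are can look again at those places and call weak uptake that would otherwise be passed over. The same reader may also be slower to call equally weak uptake where the CT/MRI shows nothing. Both effects push the two methods towards agreement, and the first raises sensitivity when CT/MRI-visible lesions are the reference.

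There is room for this here. Section 2 reports SUVmax from 1.6 to 19.3 in the earlier five-patient series, and the plan sets no threshold for a positive site. Calls at the faint end therefore rest on judgement.

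Section 2 also says these pilot data may inform the planning of later studies, so an inflated sensitivity could be carried forward. The problem cannot be repaired at analysis: once a reader has seen the CT/MRI, only a fresh read by someone else would be independent.

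**Working it through.** **1. Can the plan be followed with an unmasked read?**

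| Question | Where | Answer |
|---|---|---|
| Does the comparator exist before the PET read? | 4.2, criterion 3 | Yes, always |
| Are PET sites compared with it? | 3 and 9 | Yes |
| Which read is described? | 12 | A radiology report |
| Is a separate research read described? | 7, 8, 9, 12 | No, but not excluded |
| Reading order, positivity rule or masking? | 7, 8, 9 | None stated |
| Does the reader have the CT/MRI? | Whole protocol | Not stated either way |

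The plan permits an unmasked read. It does not say that one takes place.

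**2. How large could the effect be?**

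The documents give no sensitivity, precision target or power for the 35 patients, so there is no planned figure to reproduce. What follows is illustration only. Let

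- S = sensitivity under a masked read (assumed 60%, 70%, 80%);
- f = share of lesions missed on a masked read that are called once the reader knows the CT/MRI (assumed 10%, 25%, 50%).

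Reported sensitivity = S + f(1 − S), so the bias is f(1 − S).

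| S | f = 0 | f = 10% | f = 25% | f = 50% |
|---|---|---|---|---|
| 60% | 60% | 64% (+4) | 70% (+10) | 80% (+20) |
| 70% | 70% | 73% (+3) | 77.5% (+7.5) | 85% (+15) |
| 80% | 80% | 82% (+2) | 85% (+5) | 90% (+10) |

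For example, with S = 70% and f = 25%: 0.70 + 0.25 × 0.30 = 0.775. The non-zero grid runs from +2 to +20 points.

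**3. Scale against sampling error.**

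With one observation per patient (ignoring several lesions within a patient), 24/35 = 68.6% has an exact 95% interval of 50.7% to 83.1%, about −18 to +15 points. Most of the illustrated shifts are smaller than that. The difference is that the shift does not shrink with more patients or lesions, and no confidence interval shows it.

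**4. How much would a locked read remove?**

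Section 8, step 5 acquires a CT together with the PET, so some anatomical cueing remains. If a share r of misses is still upgraded from that CT, the remaining bias is r(1 − S) and the part removed is (f − r)(1 − S). With S = 70%, f = 25% and an assumed r = 10%, reported sensitivity falls from 77.5% to 73%: 4.5 of the 7.5 points are removed.

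**The case against.** The strongest reply is that the protocol is silent rather than wrong. No passage says the PET reader sees the staging CT/MRI, and Section 12 is about disclosure: it does not say that the clinical report is the source of the research site list. Section 9 plans research outputs of its own (site counts, SUVmax) and Section 11 stores imaging data in REDCap, so a separate research read could exist. A reader might infer from Section 12 that scans are read clinically with the CT/MRI in hand and that sensitivity is therefore biased upward. The documents support neither step as fact. This part of the objection stands, and the point has to be conditional.

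It is also true that no reference standard is defined. Section 9 names histology, and explores recurrence and progression, alongside conventional imaging. Where those serve as the reference, knowing the CT/MRI is not the same as knowing the reference, and the argument is weaker.

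Nor does the earlier series prove the mechanism. Section 2 reports more lesions on PET/CT than on conventional imaging. An SUVmax of 1.6 is the low end of uptake that was detected, not evidence of lesions missed until CT pointed to them.

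Finally, this is a hypothesis-generating pilot with no predefined analyses. That lowers the urgency. It does not remove the gap, because sensitivity is the first listed objective and an independent read has to be arranged when the scan is read.

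**Conclusion.** The plan does not protect the PET read from knowledge of the imaging it is compared with, and it can be followed to the letter in a way that builds in agreement. That much follows from the documents.

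Whether overestimation would occur depends on two conditions that the documents leave open: that the reader has the staging CT/MRI, and, for sensitivity, that CT/MRI-visible lesions form the reference. If both hold, the expected direction is upward. The size cannot be fixed from the documents. The +2 to +20 points rest wholly on the assumed S and f, and the shift is zero if f = 0.

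This is a change the sponsor should make, not a flaw that invalidates a descriptive pilot.

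A related but separate matter is that PET results are released and, as Section 12 acknowledges, "may prompt additional confirmatory imaging and/or invasive procedures that would not have otherwise been contemplated". Later verification is therefore not independent of PET either, and a masked first read does not address that.

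**What to change.** Add to Section 9:

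> The PET/CT reader records the PET-positive sites (location, SUVmax) in REDCap and locks the list before opening the staging CT/MRI images or report. The locked list is used for objectives 1 and 2. The clinical report may then use all imaging.

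The same single reader does both steps, so no second reader and no extra patient procedure is needed. The section should also say what makes a site PET-positive, since a locked list is only as reproducible as that rule. Section 11 limits REDCap access to the investigators and the coordinator, so a reader outside that group would need access, or the coordinator could enter and lock the list.

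Costs: protocol wording; a few minutes for each of the 35 scans; possibly a lower reported sensitivity than a clinical read would give; and a residual dependence through the CT component of the PET/CT, which should be acknowledged in the report.

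If the sponsor prefers reads made with all imaging available, Section 9 should say so, and the sensitivity and agreement results should be labelled as coming from unmasked reads.

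### The mean-SUVmax grouping for PFS has no value for a PET-negative scan, leaves the lesion set unstated, and dichotomizes uptake in a 35-patient cohort

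*Combined protocol and SAP*

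**What the plan says.** Section 3 (Objectives) lists the aim "To correlate findings on ¹⁸F-DCFPyL PET/CT with duration of progression-free survival". Section 9 (Study Statistics) gives the method: Kaplan-Meier estimates are calculated and "groups will be compared with the log-rank test". It states that "we do not have any predefined analyses in mind", but expects to dichotomize or group patients by "a number of different imaging parameters such as" "number of sites of disease, location of disease sites and mean SUV_{max} values".

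Section 9 does not define mean SUVmax. It gives no lesion set, no cut-point and no rule for a scan without a positive site. The nearest guide to the lesion set is the reporting commitment earlier in the section: "we will report the number and location of putative sites of disease detected on PET/CT".

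Section 4.1 says "we aim to enroll 35 patients". No power, alpha, hazard ratio or event count is stated for any PFS comparison. Section 2 describes the study as a pilot meant to "aid in hypothesis generation for the planning of future studies".

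**The concern.** Of the three parameters named, mean SUVmax is the only one that measures how strongly lesions take up the tracer. The other two can accommodate a negative scan: its site count is 0 and its location is none. Mean SUVmax cannot, unless a rule is added.

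Negative scans are plausible here. The earlier series in Section 2 had uptake in all five patients, but all five had metastatic clear cell disease. This study extends to localized stage II-III disease and to all histologies. Section 9 also expects to report surgical margin status and prior treatment, so some patients may have little measurable disease at the scan.

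Two things are at stake. An uptake-PFS result that silently applies only to PET-positive patients could be carried into the planning of later studies as if it applied to everyone scanned. And if the handling of negative scans, the lesion set and the cut-point are settled after PFS is known, each becomes a data-driven choice. Separately, reducing a continuous measure to two groups is costly when only 35 patients are available.

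**Working it through.** The plan gives no PFS power figure, so there is nothing to reproduce. All effect sizes, event rates and PET-negative shares below are assumptions.

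**1. How common could negative scans be?** The only figure in the documents is 0 of 5 negative. The exact one-sided 95% upper bound is 1 − 0.05^(1/5) = 1 − 0.549 = 45%. That series differs from this population, so the bound shows only that five positive scans do not rule out negatives. I used 0, 4, 7 and 11 of 35.

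**2. Does the lesion set matter?** Section 2 reports SUVmax from 1.6 to 19.3. One lesion at 19.3 gives a mean of 19.3. Adding five lesions at 1.6 gives (19.3 + 5 × 1.6)/6 = 27.3/6 = 4.55. Whether faint lesions are included can therefore move a patient across any plausible cut-point.

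**3. What does a median split cost?** For a normally distributed covariate and a modest effect, the squared correlation between the covariate and its median-split indicator is 2/π = 0.637. The split keeps about 64% of the information: 35 × 0.637 = 22.3 patients.

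**4. Simulation of the two analyses.** Settings: 35 patients; exponential PFS with median 24 months at average uptake; censoring uniform from 18 to 60 months; normally distributed uptake among PET-positive patients; two-sided 5%; 3,000 runs per setting; about 19 to 25 events. Analysis A is the log-rank test at the median among PET-positive patients. Analysis B is a Cox model in all 35 with a linear uptake term and a PET-negative indicator, testing the uptake term. The ranges cover PET-negative prognosis set to good, average and poor.

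| Hazard ratio per SD | PET-negative | A | B |
|---|---|---|---|
| 2 | 0 | 65% | 86% |
| 2 | 4 | 58–59% | 81–82% |
| 2 | 7 | 54–56% | 76–78% |
| 2 | 11 | 45–47% | 69–71% |
| 1.5 | 0 | 31% | 45% |
| 1.5 | 4 | 26–28% | 39–41% |
| 1.5 | 7 | 24% | 37–39% |
| 1.5 | 11 | 22% | 33–34% |

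The gain is about 11 to 24 points. Runs under other settings, with PET-negative patients kept or dropped, gave about 13 to 25 points in nearly every case. With no true effect (7 negative), rejection was 5.2% for A and 5.8% for B (Monte Carlo error about 0.4 points), so the gain does not come from false positives.

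Almost all of the gain comes from continuous coding. A continuous term fitted in PET-positive patients alone came within about 1 to 3 points of B. The reason to keep PET-negative patients is coverage, not power.

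**5. Would placing PET-negative patients in the low group help a two-group log-rank test?** Settings: 7 of 35 negative, high-versus-low hazard ratio 2, median 24 months in the low group, censoring at 60 months, 6,000 runs.

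| PET-negative hazard | Dropped | Placed in low group |
|---|---|---|
| Half the low group's | 39% | 68% |
| Equal to the low group's | 42% | 50% |
| Midway between low and high | 39% | 36% |
| Equal to the high group's | 40% | 27% |

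The sign of the effect depends on a prognosis that no section gives.

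**The case against.** The strongest reply is that Section 9 makes no commitment to be wrong about. Mean SUVmax is one example, nothing is predefined, and no power is claimed. The text does not say that PET-negative patients are excluded or that only PET-detected lesions are averaged. Inclusion criterion 3 requires CT or MRI within 90 days before enrolment, so SUVmax could be measured at lesions seen there, or negative scans could be assigned to the low group. Site count is listed separately and addresses burden.

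Much of this stands. The accurate statement is that the rule is missing, not that patients are dropped. The reply does not supply the rule, though: several incompatible readings fit the text, and they give different patients and different values. Measuring at CT or MRI lesions still leaves a patient with no visible lesion without a value. Exploratory status limits how much this matters, but it does not favour a two-group split over an analysis that uses the whole scale.

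A reader might infer more: that the PFS analysis discards its most informative patients and so loses power. The documents do not support that. They do not give the prognosis of PET-negative patients, and step 5 shows that including them in the low group can lower power as well as raise it. Nor must the mean give way to the highest SUVmax. The highest value is equally undefined for a negative scan, and choosing between the two is a matter of preference.

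**Conclusion.** The point holds for the mean-SUVmax grouping only, not for the PFS analysis as a whole. The missing value for a negative scan and the unstated lesion set follow from the text and need no assumption beyond the plausibility of negative scans. The cost of dichotomizing is general: about a third of the information at a median split, or roughly 11 to 24 points of power in the settings of step 4. Those figures assume that the log hazard is linear in uptake and that the hazard ratio per SD is 1.5 or 2; a strongly non-linear relation would shrink the gain.

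Severity is minor to moderate. The study is a hypothesis-generating pilot with no stated power, and its 35 patients limit any PFS comparison more than this choice does. Even with all 35 patients, the median split had only 31% power at a hazard ratio of 1.5 per SD.

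**What to change.** Add a short paragraph to Section 9, fixed before PFS data are examined:

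- State which lesions enter the uptake measure (PET-detected sites, CT/MRI lesions, or both) and the scale on which it is analysed.
- Keep PET-negative patients as their own category and report their number and Kaplan-Meier curve, without presuming the best prognosis. In the model this is an indicator alongside the uptake term, so no arbitrary background SUV is needed.
- Analyse uptake as a continuous or ordered term in a Cox model, reporting the hazard ratio with its confidence interval. Keep the Kaplan-Meier and log-rank grouping for display.
- Optionally, repeat with the highest SUVmax per patient as a sensitivity analysis.

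The cost is a few sentences and slightly more analysis work, with no new data or procedures. The linear term brings an assumption, which can be checked only roughly with about 20 events. If very few patients are PET-negative, their own hazard ratio will be too imprecise to interpret and should be treated as descriptive.
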